10.2.2.4. Assessment of Pain

At each study visit, the patient's assessment of their pain over the previous 24 hours will be recorded by study personnel using a scale of 1-10. Patients with missing visits will have their pain estimated for the missing data by averaging their pain scores reported using the formula detailed in the SAP.

10.2.2.5. Alternative Measurement of the Duration of SOM

The duration of SOM defined as the number of days from the first oral examination with WHO grade ≥ 3 through the last assessment with a WHO score ≥ 3 (and not to the first assessment with a WHO grade ≤ 3) with no further reports of a WHO grade ≥ 3 .

10.2.2.6. Duration of SOM in the Per-Protocol Population

The duration of SOM in the Per-Protocol Population defined as patients receiving a cumulative radiation dose of at least 55 Gy and having received all scheduled study drug doses.

Confidential

11. ASSESSMENT OF SAFETY

11.1. Overall Assessments

Safety in this trial will be assessed by the following comparisons between treatment groups:

- Assessment of the incidence, type, and body system categorization of AEs
- Assessment of the incidence, type, and body system categorization of SAEs
- Assessment of the changes from baseline for hematology parameters, clinical chemistry parameters, and vital signs
- Assessment of tumor progression at 12 weeks and 12 months following completion of RT classified using the RECIST tumor status system
- The incidence and severity of infections graded using CTCAE criteria
- Assessment of mortality through the 12-month post-RT clinic visit

11.1.1 Assessment of AEs

Site personnel will question and record in the eCRF all reported AEs, as defined in Section 11.2.1 that are reported between randomization through the 6 week post-RT visit. The PI will assess of the severity of the AE using the CTCAE criteria (Appendix 1). The AEs will be coded as to preferred terminology, and body system using the Medical Dictionary for Regulatory Activities (MedDRA) using a computer auto-coder and all assignments reviewed by a blinded medical reviewer. The number of events and the number of patients with each event defined by the preferred term and by body system category will be presented. Additional tables will compare the reported AEs by preferred term and body system classification classified by CTCAE severity grade (1-5) and separately by PI assessment of relationship to study drug.

11.1.2 Assessment of SAEs

Site personnel will question and record in the eCRF all reported SAEs, as defined in Section 11.2.2 that are reported between randomization through the 6 week post-RT visit. The SAEs will be coded as to preferred terminology, and body system using the Medical Dictionary for Regulatory Activities (MedDRA) using a computer auto-coder and all assignments reviewed by a blinded medical reviewer. Summary tables including the number of events and the number of patients with each event defined by the preferred term and by body system category will be presented. Additionally, the reported SAEs by preferred term and body system classification classified by CTCAE severity grade (1-5) and separately by PI assessment of relationship to study drug. A narrative summary of the patient's SAE will be included in the final Clinical Study Report.

11.1.3 Assessment of Laboratory and Vital Signs

Each of the laboratory tests outlined in Section 6.2.5 and each of the vital signs outlined in Section 6.2.6.4 will be summarized for each collection period by treatment group as:

Group mean

Original: 11 January 2017

- Group standard deviation
- Group median
- Group range

Additionally, each evaluation will be summarized as a change from baseline for each patient by treatment group as:

- Group mean
- Group standard deviation
- Group median
- Group range

Using the Central Laboratory's normal ranges and standard table of normal vital signs, each assessment will be classified as "normal", "low", or "high" and shift tables for each parameter shown of each assessment by treatment group will be displayed.

11.1.4 Assessment of Tumor Progression at 12 weeks and 12-months Post-RT

Scans at 12 weeks and 12-months post-RT will be compared to the initial images using the RECIST 1.1 system as outlined in Table 9, Table 10, and Table 11. The percent of the patients categorized as having a "complete tumor response" at 12 weeks and 12 months post-RT will be compared between the treatment groups. Additionally, the percent of the patients categorized as having a "complete tumor response" or "partial tumor response" at 12 weeks and 12 months post-RT will be compared between the treatment groups.

11.1.5 **Infections**

Patients will be assessed at each clinical visit through the 6-week post-RT visit as to the presence of probable clinical infections. All clinical diagnoses of infections will be classified as presumed fungal, presumed viral, or presumed bacterial. The severity of each infection will be graded using the CTCAE (Appendix 1). The incidence of all reported infections, the number of patients with reported infections, the number of presumed fungal, the number of presumed viral and the number of presumed bacterial infections will be compared between treatment groups. The incidence of each type of infection (fungal, viral, and bacterial) by severity grade (1-5) will be displayed.

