In the mITT population, the number of patients with RECIST evaluations categorized as complete responses to therapy was increased from 15/38 (39%) in the placebo group to 17/36 (47%) in the 1.5 mg/kg SGX942 dose group, a 21% increase. Disregarding those patients with missing or not assessed tumor status, this increase was 34% in the SGX942 1.5 mg/kg group. This is consistent with preclinical studies showing improved survival and decreased tumor volume size (3). Over the longer term, the overall resolution rate in the placebo population was high, making further improvement difficult to demonstrate. However, SGX942 definitely did not decrease the effectiveness of CRT therapy (Table 4). Similarly, the overall 1-year survival rate was similar between groups and more favorable for the SGX942 treated groups (Table 5).

Table 4: Incidence of Tumor Complete Response as a Function of Treatment Group and Timepoint (Safety Population)*

RECIST Response	Placebo n = 41	1.5 mg/kg n = 42	3.0 mg/kg n = 3	6.0 mg/kg n = 23
1-month follow-up	15/32 (47%)	17/27 (63%)	1/3 (33%)	4/16 (25%)
3-month follow-up	17/27 (63%)	18/27 (67%)	1/1 (100%)	9/17 (53%)
6-month follow-up	19/24 (79%)	19/28 (68%)	1/1 (100%)	10/14 (71%)
9-month follow-up	6/8 (75%)	14/16 (88%)	2/2/ (100%)	1/3 (33%)
12-month follow-up	22/23 (96%)	19/23 (83%)	1/2 (50%)	10/12 (83%)
LOCF** through 12-month follow-up	26/35 (74%)	28/35 (80%)	1/3 (33%)	13/22 (59%)

^{*}Percentage calculation excludes missing/not assessed evaluations

Table 5: Mortality (ITT Population¹)

Mortality	Placebo	1.5 mg/kg	3.0 mg/kg	6.0 mg/kg
	n = 43	n = 41	n = 3	n = 24
Through 12-month follow-up	9 (21%)	3 (7%)	0	4 (17%)

¹ Includes one patient dying 373 days after receiving their last study drug dose

[figure not shown]
Original: 11 January 2017 Amendment 1: 29 November 2017 Amendment 2: 22 January 2018 Amendment 3: 17 September 2019

^{**} Last Observation Carried Forward

The survival curves for the 1.5 mg/kg SGX942 and placebo groups are shown in Figure 5.

Figure 5: Survival Curve

[figure not shown]

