In this Phase 2 trial, confidence in the benefit of SGX942 is based not only on the magnitude of reduction in the duration of SOM and the concordance of the patient results with both qualitative and quantitative animal model data, but also in the internal consistency of the trial data. The duration data, AUC data, and incidence data consistently trend in the same direction and are similar across analysis populations (i.e., per protocol [PP], mITT, and ITT populations) as well as across subpopulations of groups defined by baseline characteristics (i.e., cisplatin treatment, HPV tumor status, age, sex, race, and prior tumor surgery). The additional findings of an increase in the number of patients with RECIST defined "complete response" and a reduction in the number of infections in the SGX942 dose groups are consistent with the animal model studies and strongly support the evidence for biologic activity of the drug in this patient population.

With its rapid degradation yet extended PD impact, the PK profile of SGX942 is of limited utility. Nonetheless, evaluating PK in a subset of patients demonstrated a roughly or greater than dose proportional response in C_{max} and area under the concentration time curve (AUC) of SGX942 in blood in response to increased dose levels (i.e., 1.5 vs. 6.0 mg/kg). There was no evidence of accumulation over multiple doses. These results were consistent with the nonclinical and Phase 1 clinical PK results.

Comparison of the AEs and SAEs across the dose groups (i.e., 1.5, 3.0, and 6.0 mg/kg) did not reveal any substantive differences in the incidence, severity, PI judgments as to relatedness or severity of the AEs, or specific AEs. The infusion procedures themselves were well tolerated. Complete resolution of tumor burden was similar or improved in the SGX942 1.5 mg/kg treatment group and all-cause mortality was also similar across treatment groups, with the best outcome in the 1.5 mg/kg SGX942 treatment group. SGX942 administration at all dose levels appeared to be safe and well tolerated.

[figure not shown]

Confidential

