5.3. Safety Objectives

Safety objectives will include the following:

- To assess the impact that SGX942 has on the Adverse Events (AE) and serious Adverse Events (SAE)
- To assess the impact that SGX942 has on changes in safety laboratory values
- To assess the impact that SGX942 has on the Response Evaluation Criteria in Solid Tumors (RECIST) categorization of the primary tumor at 12 weeks and 12 months CRT
- To assess the impact of SGX942 on the incidence of reported presumed bacterial
 infections between Baseline and 6 weeks after completion of radiation therapy (RT) by
 total number and by severity of infection, graded using the National Cancer Institute's
 (NCI's) Common Terminology Criteria for Adverse Events (CTCAE)
- To assess the impact of SGX942 on 12 month all-cause mortality
- To assess the impact of SGX942 on progression free survival through 12 months

Amendment 2: 22 January 2018 Amendment 3: 17 September 2019

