6.2.1 Oral Mucositis (OM) Grading

OM will be evaluated by personnel trained in the use of the WHO Oral Mucositis Grading system which includes both physical and functional information. This grading system is widely utilized in OM clinical research trials including the Phase 2 trial and is shown in Table 8.

Score	Findings		
0	No findings OR Pain or erythema (not both)		
1	Pain and erythema AND No ulcer		
2	Ulcer and/or pseudomembrane, AND Able to eat solid food AND Able to drink		
3	Ulcer and/or pseudomembrane, AND Not able to eat solid food AND Able to drink		
4	Ulcer and/or pseudomembrane, AND Not able to eat solid food AND Not able to drink		

Table 8: WHO Oral Mucositis Grading System

Only medical personnel at the site who have undergone training and certification in using the WHO Grading system will perform the OM assessments.

6.2.2 **Tumor Status**

The tumor response to treatment will be used as a safety endpoint. Results at 12 weeks and 12 months post-RT will be compared to the Screening results using the RECIST 1.1 system. The evaluation criteria for the target lesion (the primary head and neck carcinoma) are shown in Table 9; the criteria for non-target lesions are shown in Table 10; and the criteria for overall categorization of the tumor status are shown in Table 11. In addition, details pertaining to recurrence of disease, additional therapy, or surgery required after the active treatment phase of the trial is completed will be collected and recorded in the eCRF throughout all follow up visits until 12 months following the last RT treatment.

Confidential

Original: 11 January 2017 Amendment 1: 29 November 2017

Amendment 2: 22 January 2018 Amendment 3: 17 September 2019

Table 9: RECIST Evaluation of the Target Lesion

Target Lesion Response	Measurement	
Complete Response (CR)	All target lesions gone	
Partial Response (PR)	>30% decrease from baseline	
Progressive Disease	>20% increase from smallest sum of longest diameter recorded since treatment started (best response)	
Stable Disease (SD)	Neither Progressive Disease nor Partial Response	

Table 10: RECIST Evaluation of the Non-target Lesion

Target Lesion Response	Measurement	
Complete Response (CR)	All non-target lesions gone Tumor markers gone	
Stable Disease (SD)	Persistence of ≥1 non-target lesion Tumor marker level elevated	
Progressive Disease	Enlargement of non-target lesions	

Table 11: Overall RECIST Response

Target Lesions	Non-target Lesions	New Lesions	Overall Response

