12. STATISTICS

12.1. Overview

Complete details of analyses and relative order of importance of each analysis are more fully delineated in the Statistical Analysis Plan.

Given the anticipated non-Gaussian distribution of values for duration of OM, the severity-weighted OM calculations (AUC), and the days to onset of OM, treatment groups will be compared for these variables using a log-rank test of the differences in the duration of SOM between the SGX942 and placebo treated groups. The incidence of OM, percent of RECIST complete responders, and percent of patients with each category of infection will be compared using chi-squared tests. The primary analysis population will be patients who have received enough radiation exposure to put them at significant risk of developing SOM (defined as a cumulative radiation dose of at least 55 Gy).

Original: 11 January 2017 Amendment 1: 29 November 2017

Amendment 2: 22 January 2018 Amendment 3: 17 September 2019

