**Table 6: Standard Criteria for Vital Signs** 

## 10.4 ASSESSMENT OF TUMOR PROGRESSION

Scans at 12 weeks and 12-months post-RT will be compared to the initial images using the RECIST 1.1 system as outlined in Tables 3, 4, and 5 and compared for overall classification as well as the target and non-target lesion evaluations. The number and percentage of patients in each overall response category will be summarized by treatment group.

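### The 12-month tumour-response comparison judges the scan alone, so a tumour cleared by later surgery or new therapy counts as a complete response, and death or a missing scan has no stated handling

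*Protocol*

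**What the plan says.** Tumour response at 12 weeks and 12 months is a named safety objective: Protocol 5.3 refers to RECIST "categorization of the primary tumor at 12 weeks and 12 months CRT". Protocol 11.1.4 gives the method: "Scans at 12 weeks and 12-months post-RT will be compared to the initial images using the RECIST 1.1 system". It compares percent CR, and percent CR or PR, between arms at each time. Protocol 12.1 gives the test: "percent of RECIST complete responders, and percent of patients with each category of infection will be compared using chi-squared tests". SAP 10.4 is descriptive: "The number and percentage of patients in each overall response category will be summarized by treatment group". SAP section 10 places safety analyses in the Safety Population.

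In Protocol Table 9 and SAP Table 3, target-lesion CR requires only that the target lesions have disappeared, whatever removed them. The overall-response tables (Protocol Table 11, SAP Table 5) have no category for death, for no scan, or for treatment received before the scan.

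The events needed for such a rule are collected. Protocol 6.2.2 says that details of "recurrence of disease, additional therapy, or surgery required after the active treatment phase of the trial is completed will be collected", through 12 months. Protocol 6.3.10 records vital status, recurrence and new anti-cancer therapy at monthly contacts. The response analysis uses none of these.

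**The concern.** The objective asks whether a drug given during chemoradiation impairs tumour control. A scan at month 12 shows whether tumour is visible then. It does not show whether chemoradiation controlled it or whether a failure was later operated on or retreated. Classified by the scan alone, a rescued failure looks the same as a success.

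If failures are rescued at similar rates in both arms, a real deficit is diluted. If they are rescued more often in the arm with more failures, the deficit can disappear or reverse. Patients who die before the scan add a second uncertainty, because the text does not say whether they stay in the denominator as non-responders or leave the percentage. A similar 12-month CR rate in the two arms could then be read as reassurance that it does not give.

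**Working it through.** **1. Patient histories against each analysis, as written**

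| History | 12-week response | 12-month response | Protocol PFS (11.1.7) | SAP PFS (10.7) | Mortality |
|---|---|---|---|---|---|
| Residual tumour resected before the 12-week scan, clear afterwards | CR | CR | No event unless imaging before surgery reported less than CR | No event unless more chemotherapy or a recorded recurrence or new cancer | No event |
| Residual tumour on the 12-week scan, then resected, clear at 12 months | Not CR | CR | Event at 12 weeks | No event unless more chemotherapy or a recorded recurrence or new cancer | No event |
| Recurrence after week 12, resected, clear at 12 months | CR | CR | Event only if imaging reported it | Event | No event |
| Death between the scans | As scanned | No rule | Event | Event | Event |
| Untreated recurrence visible at 12 months | As scanned | Progressive disease if beyond the threshold from the smallest sum, or a new lesion | Event | Event | No event |

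The first three rows are all CR at 12 months. Measuring progression from the smallest sum, and the new-lesion rule, catch tumour still visible on the scan. They do not reclassify tumour already cleared.

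**2. Phase 2 figures for the same measure** (Protocol 4.5, Table 4, placebo v 1.5 mg/kg)

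The footnote reads "Percentage calculation excludes missing/not assessed evaluations". The 12-month entries reproduce: 22/23 = 95.7% v 19/23 = 82.6%, difference -13.0 points (chi-squared p = 0.155, Fisher p = 0.346). Left out are 41 - 23 = 18 and 42 - 23 = 19 patients. With all treated patients as denominator: 22/41 = 53.7% v 19/42 = 45.2%, difference -8.4 points.

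Table 5 gives 9/43 = 20.9% and 3/41 = 7.3% deaths. Tables 4 and 5 use different populations (Safety and ITT), so what follows assumes that all these deaths were in the Safety Population and lacked a 12-month scan.
- Scanned patients plus deaths as non-CR: 22/(23 + 9) = 68.8% v 19/(23 + 3) = 73.1%, difference +4.3 points (Fisher p = 0.778).
- Alive without a scan: 41 - 23 - 9 = 9 v 42 - 23 - 3 = 16. With these patients as non-response in both arms the rates are 22/41 v 19/42 (-8.4 points). With them as response in both arms they are 31/41 = 75.6% v 35/42 = 83.3% (+7.7 points).

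**3. Dilution by later treatment** (assumed figures)

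Let p be the CR rate without further treatment and s the share of failures cleared before the scan. Scan CR = p + (1 - p)s. With the same s in both arms, the observed difference is (1 - s) times the true one. Take 75% on placebo v 65% on active, 130 per arm, all scanned:

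| s | Scan CR | Difference | Power |
|---|---|---|---|
| 0 | 75.0% v 65.0% | -10.0 points | 42% |
| 0.25 | 81.3% v 73.8% | -7.5 points | 30% |
| 0.50 | 87.5% v 82.5% | -5.0 points | 20% |
| 0.75 | 93.8% v 91.3% | -2.5 points | 12% |

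Equal shares cannot change the sign; unequal shares can. With s = 0.25 on placebo, the arms are level when 0.35(1 - s) = 0.25 x 0.75 on active, that is s = 0.46. A higher share on active reverses the sign.

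**4. Deaths outside the denominator** (assumed)

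Take 130 per arm, deaths of 7% on placebo v 21% on active, and scan CR of 90% among survivors in both arms. Scan-only CR is 109/121 = 90.1% v 93/103 = 90.3%. With deaths as non-response it is 109/130 = 83.8% v 93/130 = 71.5%, difference -12.3 points (p = 0.017). The separate mortality comparison, 9/130 v 27/130, would show this harm itself (chi-squared 10.4, p = 0.001).

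**The case against.** **Tumour control does not rest on this endpoint.** Mortality and PFS are prespecified safety analyses. Deaths are compared by chi-squared and log-rank tests. SAP PFS counts recurrence, new cancer and more chemotherapy. Protocol PFS counts any imaging result below CR, so residual tumour on the 12-week scan is a failure before later surgery can erase it, and the same patient is a non-responder in the 12-week comparison. This stands, and it narrows the point to one endpoint. It does not make the 12-month comparison interpretable: neither PFS definition names surgery, the two disagree on what progression is, and the first history in step 1 can pass every analysis as a success.

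**The plan does not say that deaths are dropped.** A reader might infer this from the Phase 2 footnote, but that footnote belongs to another trial's table. Protocol 11.1.4 speaks of the percent of patients, and the SAP sets the Safety Population; read literally, the dead remain as non-responders. The defect is an unstated denominator, not a stated exclusion.

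**Phase 2 does not demonstrate the mechanism.** A reader might take the change of direction in step 2, or the Table 4 last-observation row (26/35 v 28/35), as showing hidden harm. The counts are small and the differences tested are not significant. This plan does not propose carrying the last observation forward, and nothing attributes the missing scans to surgery or retreatment. Counting deaths moved the scanned-only comparison in the drug's favour. The figures show only that the answer depends on a rule left open.

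**Surgery before chemoradiation.** Phase 2 consistency was described across subgroups including "sex, race, and prior tumor surgery", and a reader might infer that resected patients inflate CR here. The documents give no resected share for this trial, and the listed baseline items do not name prior resection. The point cannot be sized and is not relied on.

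**Conclusion.** The concern holds for the 12-month CR and CR-or-PR comparisons as written. They classify by the scan alone, so tumour cleared by later treatment counts as response, although the plan collects the events that would identify it. Under an equal clearance share s, the true difference shrinks by the fraction s: an assumed 10-point deficit becomes 7.5, 5.0 or 2.5 points at s = 0.25, 0.50 or 0.75. The documents give no figure for s, so the actual size is unknown.

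For deaths and missing scans the plan is silent rather than wrong. In Phase 2 about 45% of treated patients were outside the 12-month percentage (18/41 and 19/42), so the choice is not minor.

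This is a worthwhile correction to a safety endpoint outside the primary analysis and the hierarchical testing. It is not evidence of harm, and it does not mean that the safety plan as a whole overlooks tumour control.

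**What to change.** In SAP 10.4, for both the 12-week and 12-month comparisons:
- Use the Safety Population as denominator.
- Count as not CR, and not CR or PR, any patient who before that scan died, had documented recurrence or progression, or received surgery or new anti-cancer therapy for residual or recurrent tumour. Surgery for another reason, including neck surgery as such, should not count automatically.
- Show patients alive without a scan as not evaluable, with bounds that take all of them as response and none as response.
- Keep the scan-only tabulation alongside.

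Reconcile the PFS definitions in Protocol 11.1.7 and SAP 10.7, and state whether surgery for residual or recurrent tumour is an event.

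The cost is SAP wording and programming, with the PFS change carried into the protocol. Vital status, recurrence, further therapy and surgery are already collected, and no visit changes. Reported response rates will be lower than under scan-only classification, and the revised endpoint will overlap somewhat with PFS. The rules should be fixed before unblinded results are seen, since they can alter the direction of the comparison.
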